- 1.21 SDF applied with Super Floss can reliably arrest and/or remineralize initial interproximal lesions.
- 1.22 SDF applied with Super Floss will be more effective than SDF applied without Super Floss or fluoride varnish applied alone in arresting initial interproximal caries.

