2.0 OBJECTIVES AND PURPOSE

- 2.1 The primary aim of this prospective study is to test if 38% SDF application using Super Floss can reliably arrest caries in superficial interproximal lesions as determined by comparing time lapse bitewing radiographs.
- 2.2 The secondary aim is to test if SDF applied with Super Floss will be more effective than SDF applied without Super Floss or fluoride varnish applied alone in arresting initial interproximal caries also as determined by comparing time lapse bitewing radiographs.

3.0 STUDY DESIGN

- 3.1 Caries criteria is defined into 5 groups based on the zone of radiolucency using the International Caries Classification and Management System (ICCMS)¹⁸. This classification will be used by the present study to describe whether carious lesions have progressed based on comparing radiographs taken over time¹⁹ and allow for statistical analysis. The positioning of these bitewing radiographs must be consistent in showing the contact area and preventing overlap in the proximal teeth in question. ICCMS Classification is described as follows (Appendix I):
 - i. 0: No radiolucency/no caries not included in study
 - ii. RA: Initial Stages These are the target interproximal lesions for the present study
 - 1: Radiolucency in the outer half of enamel,
 - 2-Dentin-enamel Junction (DEJ): lesions extending within the inner half of enamel but not to DEJ,
 - 2+DEJ: lesions extending within the inner half of enamel including the DEJ,
 - 3: lesions extending to the outer one-third of dentin past the DEJ, and

- iii. RB: Moderate Stages and beyond These lesions will not included in present study because it is currently the standard of care to provide appropriate dental restorative treatment to repair the caries.
- 3.2 Each child with interproximal lesions on deciduous molar teeth meeting eligibility criteria RA Category 1, 2, or 3 will be invited to participate. Those who agree to participate will be randomly allocated to one of three treatments: Fluoride varnish (Control) application alone versus SDF application without Super Floss (Control) versus SDF application with Super Floss (Intervention). Daily flossing and oral hygiene instruction will be taught to patients of all study groups. Inclusion, Exclusion, and Withdrawal criteria are below in Section 5.

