13.0 STATISTICAL CONSIDERATIONS

- 13.1 The proposed pilot Phase III randomized controlled clinical trial aims to determine which of the following treatments is superior in arresting dental caries among patients presenting with interproximal caries scoring RA1 RA3 on the International Caries Classification and Management System (ICCMS): (1) Fluoride varnish (FV, current standard of care, control), (2) Super floss + SDF + FV, (3) SDF + FV. We hypothesize that group 2 will have the best outcomes, as measured by no change or reversal in ICCMS classification indicating no caries progression or remineralization on radiographic examination, (higher score indicates progression) followed by group 3. As we could find no data on ICCMS-defined progression or remineralization rates for either Super Floss or fluoride, we were unable to calculate power. Instead, we provide estimates of recruitment based on feasibility. We expect to accrue approximately 20 participants, with 2 qualifying teeth per participant, in each group.
- 10% loss to follow up has increased dramatically to ~48%. Given this unexpected setback, we now need to continue recruiting participants to reach sufficient power. We originally planned to enroll 39 subjects in the study, but would now like to add 21 new participants for a total of 60 participants.

Descriptive statistics will be calculated for all demographic and clinical characteristics to assess the degree to which randomization was successful using means and standard deviations or medians and interquartile ranges for continuous variables and counts and percentages for categorical variables.

The primary analysis will be by intent-to-treat. The primary outcome is the change in ICCMS category, as assessed by radiographic evidence, from baseline to 12 months, with a planned interim analysis to evaluate the endpoint at 6 months for early indications of efficacy. We will calculate the median difference at each time point and use an individual-level model with an adjustment to the standard error to account for the clustering. First we will evaluate the association between treatment groups and the change in ICCMS score from baseline at 6 and 12 months using a cluster-adjusted chi-squared test. We will further assess

14

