the relationship between these two variables using generalized estimating equations, specifying a Poisson (or negative binomial, if overdispersed) family and a log link. We will also specify an exchangeable correlation matrix and a robust standard error.

Since the study is randomized, we do not anticipate needing to adjust for any confounders. However, should we find any differences in demographic or clinical variables at baseline, we will investigate them as potential confounders, which will be defined as those variables which alter the odds ratio by >15% when included in the model.

For those with missing data on outcomes or other covariates to be included in the model, we will consider multiple imputation methods if the amount of missing data is <10%. To assess the impact of missing data, we will compare those with missing data to those not missing data with respect to demographic and clinical variables to assess comparability. Should imputation be utilized, a sensitivity analysis will be conducted excluding those for whom data was imputed to assess the impact of imputation.

Model fit will be evaluated by inspection of residuals and influential points. As we are conducting an interim analysis, we will use a two-sided Bonferroni-corrected p-value of a=.025 for statistical significance. Finally, to assess the degree to which the two raters agree with respect to classifying the outcome of the x-rays, we will calculate and report Kappa. All statistical analyses will be done using Stata 15.0 (College Station, TX).

Power Analysis

We calculated power using a cluster-randomized design. We were unable to locate any previous studies examining the impact of these three treatments (or any two) using the same classification system as our outcome. However, we were able to obtain an estimate of 0.0 to 0.25 for the interclass correlation coefficient (ICC) (Honkala et al., 2011). Assuming the mean ICC, and assuming a clinically significant mean difference of 0.2, a standard deviation of 0.2, a covariance of cluster sizes of 0.65, two caries on average per child, and a two-sided adjusted Type I error rate of 0.025 to account for the three time points at which the data will be analyzed, we will have 80% power with 11-12 participants per group, for a total of 33-36 participants (66-72 caries). Since we anticipate significant loss-to-follow-up over the course

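### Does the 0.025 significance level need a further multiplicity rule for the pairwise comparisons between the three arms?

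*Combined protocol and SAP*

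**What the plan says.** On alpha, Section 13.0 gives one rule: "As we are conducting an interim analysis, we will use a two-sided Bonferroni-corrected p-value of a=.025 for statistical significance". The interim analysis is described as "with a planned interim analysis to evaluate the endpoint at 6 months for early indications of efficacy", and the primary outcome is the change in ICCMS category from baseline to 12 months. The Power Analysis paragraph uses the same 0.025 but attributes it to three time points. Section 10.0 shows that the third of these is baseline.

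On tests, Section 13.0 states: "First we will evaluate the association between treatment groups and the change in ICCMS score from baseline at 6 and 12 months", by a cluster-adjusted chi-squared test. It then examines "the relationship between these two variables using generalized estimating equations". Neither step names a contrast between two particular arms.

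On aims, hypothesis 1.22 expects that "SDF applied with Super Floss will be more effective than SDF applied without Super Floss or fluoride varnish applied alone" will be the result, and Section 2.2 makes this the secondary aim: "The secondary aim is to test if SDF applied with Super Floss will be more effective than SDF applied without Super Floss or fluoride varnish". Section 13.1 goes further. It says the trial "aims to determine which of the following treatments is superior in arresting dental caries", and adds: "We hypothesize that group 2 will have the best outcomes", with SDF without Super Floss next. Section 13.1 also calls the trial a pilot, and Section 12.0 calls it small and preliminary.

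**The concern.** A three-group test can show that the arms differ but not which arm is better. The aims in 1.22, 2.2 and 13.1 therefore seem to need pairwise results. Halving 0.05 for two looks leaves nothing for several arm comparisons, and the plan does not make pairwise claims conditional on the three-group test, put them in order, split alpha between them or label them exploratory. The words that introduce the chi-squared test and then the GEE give a sequence of analyses, not a condition. The predicted ranking is an expectation, not a testing order.

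If every pair were tested at 0.025 at each look and any significant result were claimed, the two-sided family-wise error would exceed 5%. A reader could not tell whether such a claim was confirmatory, and the choice of which contrasts count could be made after seeing the data.

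**Working it through.** **1. The plan's own figures.** Alpha: 0.05/2 = 0.025, which matches; 0.05/3 = 0.0167 does not. So the level belongs to the two post-baseline analyses, and the mention of three time points is a slip that changes no number.

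Sample size, from the Power Analysis: difference 0.2, SD 0.2, two lesions per child, cluster-size variation 0.65 (read as a coefficient of variation), mean ICC (0.0 + 0.25)/2 = 0.125, 80% power, two-sided 0.025.

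- Lesions per arm: 2 × (2.2414 + 0.8416)² × (0.2/0.2)² = 19.01
- Design effect: 1 + ((1 + 0.65²) × 2 − 1) × 0.125 = 1.2306
- Children per arm: 19.01 × 1.2306 / 2 = 11.70

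This matches the stated 11-12 per group. The study is sized for one two-arm contrast at 0.025.

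**2. False-positive rates.** Three equal arms, no true difference, normal test statistics, two-sided 0.025 (|z| > 2.2414; three-group chi-squared on 2 df > 7.378), by simulation. The correlation between the looks is not in the documents, so 0.9 to 0.3 is assumed.

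| Claims counted | Both looks | 12 months only |
|---|---|---|
| One contrast | 3.6% to 4.8% | 2.5% |
| Three-group test | 3.7% to 4.9% | 2.5% |
| Two Super Floss contrasts, ungated | 6.7% to 8.9% | 4.6% |
| All three pairs, ungated | 9.1% to 12.2% | 6.4% |
| All three pairs, only after a significant three-group test | 3.7% to 4.9% | 2.5% or less |

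The excess over 5% needs two things the plan does not specify: ungated pairwise tests, and either claims at both looks or all three pairs.

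**3. What a written rule would cost.** Power for Super Floss against varnish at one look, with the plan's inputs and a normal approximation. In the first pattern Super Floss beats both other arms by 0.2; in the second, SDF without Super Floss lies halfway.

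| Rule | 12 per arm: beats both / halfway | 10 per arm: beats both / halfway |
|---|---|---|
| None | 81% / 81% | 73% / 73% |
| Fixed order, varnish contrast first | 81% / 81% | 73% / 73% |
| Holm over the two contrasts | 78% / 74% | 69% / 64% |
| Alpha split, 0.0125 each | 73% / 73% | 64% / 64% |
| Gate, 2 df | 78% / 71% | 68% / 61% |
| Gate, 4 df (three change categories, same noncentrality assumed) | 71% / 59% | 60% / 49% |

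Ten per arm is about what 48% loss leaves from 60 recruited: 60 × 0.52 / 3 = 10.4.

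The ranking changes with the contrast. For Super Floss against SDF without it, when Super Floss beats both arms at 12 per arm, the varnish-first order gives 70% and the 2-df gate 78%; in the halfway case both give about 24%. With the order reversed, the halfway case cuts Super Floss against varnish from 81% to 24%. The gate's cost also depends on how ICCMS change is grouped, which the plan leaves open.

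**The case for a change.** The strongest case for a change is that the plan chose to control false positives with a Bonferroni correction, describes itself as Phase III as well as pilot, and in 13.1 sets out to name the superior treatment. Having made that choice, it should say which claims the control covers. A few sentences would do so at the same alpha and the same 11-12 per group. Counting only false claims that Super Floss is better gives 3.3% to 4.4% over both looks, but that does not answer the point, because the tests are two-sided and a false finding against Super Floss is also an error.

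Much of this stands. No multiplicity policy for the arms is written down, the error rates reproduce, and nothing in the text makes the three-group test a gate.

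It does not follow that the plan must adopt a rule. The inflated rates describe tests the plan does not list. A written rule also has a price: at 12 per arm a gate can cost Super Floss against varnish up to 22 points (81% to 59%). A varnish-first order avoids that loss but makes the other named contrast depend on the first. Choosing among these rules, or reporting secondary contrasts with intervals and no formal control, is a judgement on which statisticians would reasonably differ in a trial of this size.

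**Conclusion.** The omission is real but calls for no change. The level of 0.025 does what Section 13.0 says it does: it holds about 5% over the two looks for one contrast or for the three-group test. The two named contrasts belong to the secondary aim and total 4.6% at the 12-month primary time point. The rate of 6.7% to 8.9% arises only if both contrasts are claimed ungated at both looks. In a self-described small, preliminary pilot, treating the pairwise results as secondary is a sensible way for analysts to fill the gap. The competing formal rules are a trade-off with no clear winner. The three-time-points wording is clerical: correcting it alters no alpha, sample size or result.

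This rests on an assumed between-look correlation of 0.3 to 0.9, on one decisive test per look (the plan lists both a chi-squared test and a GEE), and on normal approximations that are optimistic with so few children. A t-based check gives about 76% rather than 81% power at 12 per arm. The conclusion would be weaker if a report presented ungated pairwise results at both looks as confirmatory.

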of the study, we will inflate the sample size by ~48% and recruit a total of 54-60 participants (108-120 caries). Sample size was calculated using PASS Software v.14.0 (Kayesville, UT).

This study is powered to detect an effect in a population of children who are predominantly non-white. Therefore, the sample size as calculated is likely to result in a sample size with reasonable power to detect an effect near the size outlined above, if perhaps slightly larger.

14.0 REGISTRATION GUIDELINE

- 14.1 Participants will be randomized as described in Section 6.3. Randomization envelopes will be available to the investigators, who need only select the next one in the series to accomplish randomization. No stratification parameters have been specified.
- 14.2 The forms and records needed for registration: Informed Consent; Assentfor Younger Subjects ; and Tracking Form.

Note: At the time of registration, two copies of a signed and dated patient Informed Consent form with Bill of Rights must be available (a copy for patient's dental chart; a copy for the subject/parent; and the original for the PI's file).

15.0 BIOHAZARD CONTAINMENT

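### The stated 80% power is not delivered: whole-category scores with means 0.2 apart cannot have an SD of 0.2, and 54-60 recruits do not cover a 48% loss in all of them

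*Combined protocol and SAP*

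**What the plan says.** Section 13.0 defines the endpoint: "The primary outcome is the change in ICCMS category" from baseline to 12 months, analysed per lesion with a standard error adjusted for clustering within child. Section 5.1.2 and Appendix I give the scale in whole categories.

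The Power Analysis takes the ICC from a cited source ("we were able to obtain an estimate of 0.0 to 0.25 for the interclass correlation coefficient (ICC"), uses its mean, and proceeds "assuming a clinically significant mean difference of 0.2, a standard deviation of 0.2", with a cluster-size variation of 0.65, two lesions per child and two-sided alpha 0.025. It gives no source for the SD. It concludes: "we will have 80% power with 11-12 participants per group, for a total of 33-36 participants (66-72 caries". For attrition it adds: "we will inflate the sample size by ~48% and recruit a total of 54-60 participants (108-120 caries".

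Earlier in the same section, 13.1 says "we were unable to calculate power. Instead, we provide estimates of recruitment based on feasibility". The next paragraph reports that "10% loss to follow up has increased dramatically to ~48" per cent and justifies going from 39 to 60 children because "we now need to continue recruiting participants to reach sufficient power".

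**The concern.** A difference of 0.2 with an SD of 0.2 is a standardized effect of 1.0. On a continuous scale that would only be optimistic. On a scale of whole steps, the mean restricts how small the variance can be, so the pair may be impossible. The attrition step also appears to multiply by the loss rate instead of dividing by the retained fraction.

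The 80% figure supports the decision to recruit 21 more children, and a reader of a null result would rely on it. If true power is nearer one half, a null result says much less about the treatments than the plan implies.

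**Working it through.** **Inputs** (section 13.0): difference 0.2; SD 0.2; ICC 0.125 (midpoint of 0 to 0.25); m = 2 lesions per child; 0.65, read as the coefficient of variation of cluster size; two-sided alpha 0.025; power 80%.

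**1. The plan's figure.** z = 2.2414 + 0.8416 = 3.0830; squared, 9.505.

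Design effect = 1 + ((1 + 0.65²) × 2 - 1) × 0.125 = 1.2306.

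Children per arm = 2 × 9.505 × (0.2/0.2)² × 1.2306 / 2 = **11.70**. Without the 0.65 term the design effect is 1.125 and the result 10.69. Rounded up these give 12 and 11, matching the plan.

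**2. The smallest possible SD.** A whole-number score whose mean has fractional part f has variance of at least f(1 - f). For two equal arms with means m and m + 0.2, the average variance is smallest when one mean is a whole number: (0 + 0.2 × 0.8)/2 = 0.08, so SD ≥ **0.283**. This is reached only if all lesions in one arm have the same change (for example none) and 20% in the other differ from that by one step. The same bound applies to a binary progressed/not-progressed outcome. Counting the two sub-levels of category 2 in section 3.1 as separate whole steps does not alter it.

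**3. Sample size at that SD.** 9.505 × (0.283/0.2)² × 1.2306 = 23.4, or **24 per arm** (19.0 before rounding at ICC 0; 27.8 at ICC 0.25).

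**4. Attrition.**
- Needed if 48% of all recruits are lost: 33/0.52 = 63.5 and 36/0.52 = 69.2, so **64-70**.
- Multiplying instead: 33 × 1.48 = 48.8; 36 × 1.48 = 53.3.
- The stated 54-60 covers 1 - 33/54 = 38.9% to 1 - 36/60 = 40% loss.
- Completers at 48% loss: 54 × 0.52 = 28.1; 60 × 0.52 = 31.2 (10.4 per arm).
- If only the first 39 lose 48% and the 21 added lose 10%: 39 × 0.52 + 21 × 0.90 = 39.2 (13.06 per arm).

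Lost children cannot be counted back in: section 3.5 discards the data of dropouts, and section 13.0 considers imputation only below 10% missing.

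**5. Power for a difference of 0.2.** With k children per arm, power = Φ[(0.2/SD) × sqrt(k/DEFF) - 2.2414].

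At the plan's SD of 0.2, ICC 0.125 and 48% loss in all: 75% with 60 recruited, 70% with 54. At SD 0.283:

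| Children per arm | ICC 0 | ICC 0.125 | ICC 0.25 |
|---|---|---|---|
| 10.4 (60 recruits, 48% loss in all) | 52% | **43%** | 36% |
| 12 (the plan's target) | 58% | **49%** | 41% |
| 13.06 (60 recruits, mixed loss) | 62% | **52%** | 45% |
| 20 (60 recruits, no loss) | 82% | **73%** | 65% |

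The minimum SD is itself a best case. With an assumed SD of 0.3 to 0.5 (the documents give no observed value) and ICC 0.125, power is 38% down to 14% at 10.4 per arm and 47% down to 17% at 13.06.

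**6. Detectable difference at 80% power**, using the smallest SD possible for each difference, sqrt(d(1 - d)/2): d = q/(1 + q), with q = 9.505 × 1.2306/(2k). This gives **0.36** category at k = 10.4 and **0.31** at k = 13.06.

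**The case against.** **Attrition.** The 48% is reported as loss already seen, so it may describe the first 39 children only. They would leave 39 × 0.52 = 20.3 completers, and the 21 added could lose about 39% (for 33 completers) or 25% (for 36) with the target still met. This reading removes the attrition fault, but not the SD fault. It is also not what the Power Analysis says, which applies the 48% to the whole sample. Even on the stricter reading the shortfall is modest at SD 0.2: 75% power from 60 recruits, or 79% without the cluster-size term.

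**Scale.** If the sub-levels of category 2 were scored half a category apart, or two raters' scores were averaged, the minimum SD would fall to sqrt(0.03) = 0.173 and 0.2 would be attainable. That is correct, but no document specifies such scoring; the two raters appear only in connection with Kappa.

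**Unit.** The 0.2 might be the SD of a child's mean over two lesions. That is attainable only at ICC 0; at ICC 0.125 the minimum is 0.283 × sqrt(1.125/2) = 0.212. The plan's answer is also reproduced with 0.2 as a lesion-level SD.

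**Hedging.** The trial is called a pilot, and section 13.0 ends by allowing that the detectable effect may be slightly above 0.2. With nobody lost that would be fair: q = 11.70/40 = 0.292 gives d = 0.226. With the expected losses it is 0.31-0.36, which is not slight. The pilot label does not make a stated 80% true.

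**Method.** The figures use a normal approximation, not the planned chi-squared or GEE tests. That limitation stands, but this is the formula that reproduces the plan's own answer.

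**Conclusion.** The concern holds. The main fault is an input: for whole-category lesion scores, a difference of 0.2 and an SD of 0.2 cannot both be true. At the smallest attainable SD and the plan's ICC, 60 recruits give 43-52% power across the two loss scenarios, and 73% with complete follow-up. In the table above, only ICC 0 combined with no loss passes 80%, and the plan assumes neither.

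The attrition error is secondary and depends on the 48% applying to all recruits, as the Power Analysis words it. Separately, the 80% claim contradicts the statement in 13.1 that power could not be calculated, and it is used to justify the enlargement.

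The conclusion rests on whole-category scoring, a mean ICC of 0.125 and 0.65 being a coefficient of variation. Dropping the cluster-size term raises the 43% to 46% and the 73% to 77%, which does not change the conclusion.

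**What to change.** In section 13.0:

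- Replace the SD of 0.2 with a value of at least 0.283 and show a range such as 0.3-0.5, labelled as an assumption; or state the scoring rule (sub-levels, combination of raters) that allows a smaller SD.
- Compute recruitment as n/(1 - 0.48), and say whether 48% is expected in all 60 children or only in those already enrolled.
- Restate, for the completers expected from 60 recruits, the power for a 0.2 difference and the difference detectable at 80% power.
- Remove or correct the claims of 80% and sufficient power, and reconcile them with 13.1.

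The cost is protocol and SAP wording only. The stated power becomes less favourable. The correction does not itself require more children; whether to enlarge is for the investigators to decide.

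### At 11-12 children per group, a test that holds the two-sided 0.025 level has about 71-76% power on the plan's own inputs, not the stated 80%

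*Combined protocol and SAP*

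**What the plan says.** The Power Analysis part of section 13.0 claims that "we will have 80% power with 11-12 participants per group, for a total of 33-36 participants (66-72 caries"). It gets there by "assuming a clinically significant mean difference of 0.2, a standard deviation of 0.2", two lesions per child on average, a cluster-size variation of 0.65, and the mean of "an estimate of 0.0 to 0.25 for the interclass correlation coefficient (ICC"). The level is "a two-sided adjusted Type I error rate of 0.025 to account for the three time points", and the analysis text agrees: "we will use a two-sided Bonferroni-corrected p-value of a=.025 for statistical significance". The software is PASS 14; no formula, reference distribution or degrees of freedom is given.

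The planned model is GEE with an exchangeable correlation and a robust standard error. No small-sample correction is mentioned. Section 6.3 makes the child, not the tooth, the unit of randomisation.

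Two other statements in section 13.0 bear on the figure. Section 13.1 says "we were unable to calculate power" and offers feasibility-based recruitment estimates instead. The close of the Power Analysis speaks of "reasonable power to detect an effect near the size outlined above, if perhaps slightly larger".

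**The concern.** With 11-12 children per group, a comparison of two arms rests on 22-24 independent units. At that size a normal reference is too liberal for a cluster-robust test, and the critical value that holds 0.025 is clearly larger than the normal one. A sample size worked out with normal quantiles then overstates the power of any test that respects the level.

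The figure is used. The 33-36 evaluable children are the base for the 54-60 to be recruited, and 13.1 justifies continued recruitment by the need for enough power. If the claimed combination of 80% power and a 2.5% error rate is not available at this size, a null result will be judged against a power the trial did not have, or a positive one against an error rate it did not hold.

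**Working it through.** **Inputs, all from the Power Analysis part of section 13.0.** Difference d = 0.2; SD = 0.2; ICC = (0.0 + 0.25)/2 = 0.125; mean lesions per child m = 2; two-sided level 0.025. The value 0.65 is called a covariance of cluster sizes; I read it as the coefficient of variation (CV), which is an assumption.

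**Step 1: reproduce the plan's figure.**
- Design effect: DE = 1 + [(1 + CV²)m − 1] × ICC = 1 + (1.4225 × 2 − 1) × 0.125 = 1.2306.
- Children per group with normal quantiles: 2 × (2.2414 + 0.8416)² × (0.2/0.2)² × 1.2306 / 2 = 11.70.

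This matches 11-12 per group.

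**Step 2: power at K = 11 and 12 with different reference distributions.** The standard error is √(2 × 0.04 × DE/(2K)), which is 0.0669 at 11 and 0.0640 at 12. The noncentrality is 0.2/SE, or 2.99 and 3.12. The normal critical value is 2.24; with 2K − 2 = 20 and 22 df it is 2.42 and 2.41.

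| Reference at ICC 0.125 | 11 per group | 12 per group |
|---|---|---|
| Normal | 77.3% | 81.1% |
| t, two arms, children as units (2K − 2 df) | 71.2% | 75.8% |
| t, error pooled over three arms (3K − 3 df) | 73.3% | 77.7% |
| t, lesion-based df (4K − 2), ignores the randomised unit | 74.5% | 78.7% |

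At 13 per group (3 × 13 = 39 in total) the two-arm t gives 79.9% and the pooled version 81.4%.

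**Step 3: split the shortfall.** At 11 per group, 80 − 77.3 = 2.7 points come from rounding 11.7 down, and 77.3 − 71.2 = 6.1 points are the small-sample effect. At 12 per group the small-sample effect is 81.1 − 75.8 = 5.3 points.

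**Step 4: vary the ICC over the plan's own range** (two-arm t, children as units).

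| ICC | 11 per group | 12 per group |
|---|---|---|
| 0 | 80.6% | 84.6% |
| 0.125 | 71.2% | 75.8% |
| 0.25 | 62.9% | 67.7% |

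**Step 5: check the type of test the plan names.** Simulations used normal outcomes on the plan's inputs. A cluster-robust test with no correction and a normal reference had about 79-84% power at 11-12 per group, but a true error rate of about 4.2-5.5% across runs. With its critical value raised to hold 0.025, power was 68-71% at 11 and 73-76% at 12. A GEE with a bias-corrected robust standard error and a t reference gave 69% and 73%, with error rates of 2.5-2.9%.

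**The case against.** The strongest reply is that nothing is miscalculated: the inputs return the plan's own number, and the planned kind of test, run without correction, does have roughly 80% power. Both statements are true. A reader might infer an arithmetic slip, or that the planned GEE itself has only 71-76% power; neither is supported. What fails is the pairing of 80% power with a 0.025 level. The uncorrected test buys its power with an error rate near twice the nominal one.

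Other parts of the reply also stand:
- The normal formula is inferred. A t test with lesion-based df gives 78.7% at 12 per group and cannot be excluded as the method used. The conclusion does not depend on which was used, since every t variant in the table is below 80% at both sizes.
- Reading 0.65 as a CV is an assumption. Read as a squared CV, the two-arm t gives 69.0% and 73.7%, so the shortfall is then larger.
- A reader might infer that the plan conceals its dependence on the ICC. It does not: it says that the mean value is assumed. Only the sensitivity is missing, and it runs both ways.
- A reader might take the closing hedge as contradicting the 80% claim. It agrees with the recalculation: for a difference of 0.22, the two-arm t has 79.9% and 84.0% power.
- Sections 12.0 and 13.1 call the study small, preliminary and a pilot, and the gap is one or two children per group.

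These points limit the size of the finding. They do not restore 80% at the stated level.

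**Conclusion.** The concern holds in this form: at ICC 0.125, 80% power at a two-sided 0.025 level is not attained with 11-12 children per group by a test that holds that level. Power is about 71% and 76% (73% and 78% with error pooled over three arms), which is 4-9 points below the claim. About 3 points of the gap at 11 are rounding; 5-6 points are the small-sample effect. About 13 evaluable children per group would give 80%.

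This rests on the plan's difference, SD and ICC, on 0.65 being a CV, on pairwise comparison of two means, and on children as the independent units. The planned Poisson or negative binomial model is not the test that was powered, so the figures describe the power statement and not the power of that model. The loss-to-follow-up allowance is not examined here.

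Separately, the statement in 13.1 that power could not be calculated conflicts with the Power Analysis part of the same section, and both are current text.

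**What to change.** Three changes to section 13.0, made together:

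1. In the analysis text, specify a small-sample-corrected robust standard error for the GEE, with a t reference based on the number of children. Without this, the restated power would describe a test the plan does not use.
2. Restate the power along these lines: *With 11-12 evaluable children per group, power is about 71-76% at ICC 0.125 (about 81-85% at ICC 0 and 63-68% at ICC 0.25), two-sided 0.025, t reference on the number of children. At ICC 0.125, 80% power needs about 13 evaluable children per group (39 in total).* Name the formula and degrees of freedom, and say that 0.65 is a coefficient of variation, if that is what was meant.
3. In 13.1, remove the statement that power could not be calculated, together with the sentence offering feasibility estimates in its place. The expected accrual per group can stay.

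The closing hedge about a slightly larger effect may also stay.

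Cost: wording and one analysis specification, with no added patients. The stated power becomes less favourable by about 4-9 points, and the corrected test will reject less often than the uncorrected one.
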